Adverse Event Collection/ CTCAE Grading		Х	Х		Х	Х	Х	Х	Section 8.3	 Collect continuously at every visit and throughout the study CTCAE Version 5.0 For long-term follow-up: all SAEs regardless of relationship to study treatment and adverse events possibly related to study treatment will be collected All adverse events possibly related to study drugs or protocol procedures should be followed until they resolve, are no longer considered to be possibly related, become stable or return to baseline, the patient starts a new therapy, the patient expires, or the patient becomes lost to follow-up. The frequency of evaluation is determined according to the judgment of the investigator
Concomitant Medications		Х	x		Х	х	Х		Section 6.5	 At baseline, record prior and concurrent medications Record all pre-medications, supportive care, and concomitant medication continuously at every visit and throughout study
Lab/Diagnostic Tests	Coagulation	Х							Section 10.4 Appendix 4	 Perform at baseline and as clinically indicated Local testing

	Study Period	Baseline	Stu	Study Treatment (Cycle =28 day				ontinuation ow-Up		
	Cycle	Screening	1 a	nd 2	3	4 and Beyond (if Applicable)	Short-Term Follow-Up ^a	Long-Term Follow-Up ^a		
	Visit	0	1,3	2, 4	5	6 and Beyond (if Applicable)	801	802–8XX		
	Relative Day within a Cycle	≤28	Day 1	Day 15° (± 3)	Day 1 (± 3)	Day 1 (± 3)	Day 30 (± 7)	(± 14)		
Procedure Category	Procedure								Protocol Reference	Instructions
	Hematology	Х	Х	х	X	X	Х		Section 10.4 Appendix 4	 Assessments may be performed up to 3 days prior to Day 1 of each cycle Local testing Cycles 1 and 2 Day 15 hematology required for Arms A, C only
	Clinical chemistry	Х	х	x	Х	х	Х		Section 10.4 Appendix 4	 Assessments may be performed up to 3 days prior to Day 1 of each cycle Central testing Cycles 1 and 2 Day 15 clinical chemistry required for Arms A, C only
	FSH and estradiol levels	x				х	Х		See Section 5.1 and Section 10.4	 For Screening: local FSH/E2 testing for women <60 years when needed to confirm post-menopausal status For On study: local estradiol every 3 cycles, starting on Day 1 of Cycle 4 and again at STFU visit, for women whose postmenopausal status is due to GnRH agonist treatment
	Pregnancy test	Х					Х		Section 10.7 Appendix 7	 Local testing For Screening: serum pregnancy test required for women of child-bearing potential For on Study: per local regulations and/or institutional guidelines For Short-Term Follow-Up: local testing for women of child bearing potential

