- ^b For patients with inoperable locally advanced breast cancer: MRI scan of the breast should occur at baseline and then at the following intervals relative to Cycle 1 Day 1: every 8 weeks (±4 days) for the first 12 months and then every 12 weeks (±4 days) thereafter. For all patients: Tumor assessments, including measurement of visible lesions, CT or MRI scan of the chest, abdomen, and pelvis, should occur at baseline and then at the following intervals with first assessment relative to Cycle 1 Day 1: every 8 weeks (±4 days) for the first 12 months and then every 12 weeks (±4 days) thereafter. It is recommended that CT imaging of the abdomen and pelvis be performed with IV contrast whenever possible. If this is not feasible due to hypersensitivity or other conditions, then gadolinium-enhanced MRI is preferred. For patients with known serious allergic reactions to CT contrast material, a CT of the chest without contrast and gadolinium-enhanced MRI of the abdomen/pelvis are encouraged. For patients who discontinue study treatment without objectively measured progressive disease, continue to evaluate tumor response at the following intervals relative to Cycle 1 Day 1: approximately every 8 weeks for the first 56 weeks and thereafter approximately every 12 weeks until radiographic disease progression, death, start of a new anticancer therapy or study completion, whichever occurs first.
- c Cycle 1 Day 15: For patients assigned to Arms A or C, this visit is only for obtaining protocol-specified laboratory studies. For patients assigned to Arm B who are receiving fulvestrant, this visit is only for administration of the fulvestrant. Cycle 2 Day 15: For patients assigned to Arms A or C, this visit is only for obtaining protocol-specified laboratory studies.

Continued Access SoA for All Patients (see also Section 6.7.1)

	Study Treatment	Extension Period 30-Day Follow-Up ^a		
Visit	501-5XX	901		
Duration (days)	28	30 ±5		
Procedure			Protocol Reference	Instructions
AE Collection	Х	Х	Section 8.3	Per CTCAE v5.0, for post follow-up, the investigator should only be made aware of collected SAEs related to study regimen or protocol procedures. Collect throughout the study.
Administer study intervention	Х		Section 6.1	See Section 6.1 for Study Intervention administration details and guidelines.

Abbreviations: AE = adverse event; CTCAE = Common Terminology Criteria for Adverse Events; SAE = serious adverse event.

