10.9 Appendix 9: Liver Safety: Suggested Actions and Follow-Up Assessments	Formatted table for hepatic evaluation tests	Editorial for additional clarity
10.10 Appendix 10: Country- specific Requirements	Added appendix to include EU specific requirements for the following countries: • Belgium • Czech Republic • France • Germany • Italy, and	Regulatory request
	• Spain	

Section # and Name	Description of Change	Brief Rationale
10.10.1 Discontinuation of Inadvertently Enrolled Patients in Germany	Removed duplicate section to align with Germany appendix (Section 10.10.4)	Editorial
10.16 Appendix 16: Abbreviations	Updated abbreviations	Editorial
11 References	Updated citations	Editorial
Throughout	Minor editorial and formatting changes	Minor, therefore, not detailed

Amendment a: 8-Oct-2021

This amendment is considered to be substantial based on the criteria set forth in Article 10(a) of Directive 2001/20/EC of the European Parliament and the Council of the European Union.

Overall Rationale for the Amendment:

The primary purpose of this amendment is to incorporate a new treatment arm into the study design. Additional edits have been made to incorporate emerging data and to provide clarifications in response to site and regulatory feedback.

Section # and Name	Description of Change	Brief Rationale
Protocol Approval Page	Removed page	Medical monitor name and contact information will be provided in separate document
Title Page; 1.1 Synopsis; 1.2 Schema; 1.3 Schedule of Activities; 1.3.2 Sampling Schedules for Pharmacokinetics; 4.1 Overall Design; 6.1 Study Intervention(s) Administered; 6.1.4 Arm C Imlunestrant + Abemaciclib: General Dosing Instructions; 6.6.4 Re- escalation Criteria; 8.4 Treatment of Overdose; 8.5 Pharmacokinetics; 9 Statistical Considerations	Added treatment arm 3, imlunestrant plus abemaciclib, to study design; language added throughout protocol to reflect addition of abemaciclib to study design and analyses	New arm added to study design to incorporate abemaciclib + imlunestrant combination
1.1 Synopsis; 3 Objectives and Endpoints	Added new primary, secondary, and exploratory objectives	New objectives added for Arm C
1.3 Schedule of Activities	Added additional visits / assessments for Arms A and C	Added for abemaciclib safety monitoring
1.3 Schedule of Activities	Added clarification that patient diary is for patients randomized to Arms A or C	Clarification

Section # and Name	Description of Change	Brief Rationale

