4.1.1. Definitions

Definitions of efficacy, safety, and patient-reported outcome (PRO) analysis variables are listed in respective sections of the SAP. Other variables are listed below alphabetically:

- Age (years): age at informed consent start date; birth month and day are imputed to be 01 July because only birth year is collected through electronic case report form (eCRF).
- Baseline Measurement: unless otherwise specified, the last non-missing measurement prior to the first dose of study drug.
- Duration: duration is calculated as
 - \circ duration (days): (end date start date + 1)
 - o duration (weeks): (end date start date + 1)/7
 - duration (months): (end date start date + 1)/30.4375 (days in months = (1/12) * average number of days in a year)
 - o duration (years): (end date start date + 1)/365.25
- Duration of disease: (randomization date diagnosis of cancer date + 1)
- Study Day (safety analyses): study day is calculated as assessment date first dose date + 1 day if the assessment is done on or after the first dose day. If the assessment is done prior to the first dose day, study day will be calculated as assessment date first dose date. Date of first dose is defined as Study Day 1.

- Study Day (efficacy analyses): study day is calculated as assessment date randomization date + 1 day if the assessment is done on or after randomization. If the assessment is done prior to randomization, study day will be calculated as assessment date randomization date. Date of randomization is defined as Study Day 1, unless otherwise stated.
- Time-to-Event: the event or censoring time (days) is calculated as date of event/censoring randomization date + 1.
- Analysis Visit: analysis visit (AVISIT) will be derived according to the protocol SOA for the purpose of by-visit analyses if deemed appropriate.

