The severity of laboratory results will be classified according to NCI-CTCAE. The laboratory toxicity by worst NCI-CTCAE grade and shifts in toxicity grading from baseline to the worst post-baseline grade will be summarized. Abnormal laboratory parameters will be listed.

Shift to low/high tables will include the number and percentage of patients within each baseline category (baseline value is low, normal, high, or missing) versus each postbaseline category (worst value is low, normal, high, or missing) by treatment arm.

The analyses of adverse events, deaths, and laboratory abnormalities will be conducted in the safety population.

Time to sustained worsening of worst pain (as measured by the Worst Pain NRS) is defined as the time from randomization to the first increase (≥ 2 points) in the weekly average of the worst pain score with confirmation in the next consecutive week. See Section 4.6 for further details.

Pharmacokinetic/Pharmacodynamic Analyses

PK parameters for imlunestrant in plasma (for example, clearance, volume of distribution) and inter-individual PK variability will be computed using nonlinear mixed-effect modeling implemented in NONMEM. Covariate effects, such as age, weight, sex, and creatinine clearance, on the PK parameters of imlunestrant in plasma will also be investigated.

Biomarker data collected in this study may be used in a population PK/pharmacodynamic model.

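### Day 15 blood tests in Cycles 1 and 2 are scheduled in Arms A and C only, so the worst-grade laboratory tables are liable to overstate transient abnormalities in Arm A relative to Arm B

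*Protocol*

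**What the plan says.** Protocol Section 1.3 has a hematology row with the instruction "Cycles 1 and 2 Day 15 hematology required for Arms A, C only" and a chemistry row with "Cycles 1 and 2 Day 15 clinical chemistry required for Arms A, C only". Footnote c to the schedule agrees. On Cycle 1 Day 15 in Arm B: "For patients assigned to Arm B who are receiving fulvestrant, this visit is only for administration of the fulvestrant". On Cycle 2 Day 15: "Cycle 2 Day 15: For patients assigned to Arms A or C, this visit is only for obtaining protocol-specified laboratory studies"; it gives Arm B no such visit. All arms have these tests on Day 1 of each cycle and at short-term follow-up.

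SAP Section 4.4.2 (Laboratory Abnormalities) says: "The laboratory toxicity by worst NCI-CTCAE grade and shifts in toxicity grading from baseline to the worst post-baseline grade will be summarized". The low/high shift tables also use an extreme post-baseline category: "worst value is low, normal, high, or missing) by treatment arm". Both are produced in the safety population. SAP Section 4.1.1 defines baseline as "the last non-missing measurement prior to the first dose of study drug", so the pre-dose Cycle 1 Day 1 sample is not post-baseline.

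The SAP does not restrict these tables to visits common to the arms, adjust for the number of draws, or plan a sensitivity version. It specifies by-visit summaries for ECGs and vital signs (Section 4.7.2) but not for laboratory values.

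The amendment history in Protocol Appendix 17 records under amendment (a): "Added additional visits / assessments for Arms A and C". The reason given is safety monitoring for abemaciclib.

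**The concern.** A worst grade is a maximum. At equal underlying toxicity, a maximum over more samples can only be equal or higher, so an arm sampled more often tends to show more graded abnormalities. The extra Arm A draws fall in the first six weeks of treatment.

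Laboratory abnormalities are named under the secondary safety objective, and the tables set the arms side by side, so readers will compare A with B. Changes that come and go between Day 1 visits are the most exposed; falls in neutrophil count and rises in ALT or AST can behave this way. Some of an apparent Arm A excess in such changes could come from the schedule and not the drug. For A versus B the distortion runs against imlunestrant.

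**Working it through.** **Reproducing the plan's enrollment figure.** It is needed to see how much of Arm A was planned before three-arm randomization. From the monthly rates in SAP Section 5:

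- Months 1 to 6: 5+10+15+20+25+35 = 110, all two-arm.
- Months 7 to 14: 300 in total, of whom 15+15+18+18+36×4 = 210 are three-arm (70 per arm) and 90 two-arm.
- Two-arm stream: 110+90 = 200, so 100 in Arm A.
- At month 14, A+B = 200+140 = 340. At 45 per month A+B gains 30, so 640 is reached after 300/30 = 10 more months.
- Arm C = 70+150 = 220; total 860. This matches the SAP.

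**Counting scheduled post-baseline draws through Cycle 3 Day 1.** Arm A: C1D15, C2D1, C2D15, C3D1 = 4. Arm B: C2D1, C3D1 = 2.

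**Size at equal toxicity.** Let p be the chance that one draw shows the graded abnormality, the same in both arms. With independent draws, the share with at least one in k draws is 1−(1−p)^k. At p = 2%:

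- Arm A: 1−0.98⁴ = 7.8%
- Arm B: 1−0.98² = 4.0%
- Ratio 1.96

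For correlated draws I used an exchangeable latent-normal model with correlation ρ. For whole treatment I assumed exponential time on treatment with median 4.3 months in both arms (the planned Arm B median PFS), Day 1 draws from Cycle 2, and one follow-up draw. Both p and ρ are assumptions; the documents give neither.

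| p, ρ | Through C3D1: A vs B | Ratio | Whole treatment: A vs B | Ratio |
|---|---|---|---|---|
| 0.5%, 0 | 2.0% vs 1.0% | 1.99 | 4.3% vs 3.5% | 1.24 |
| 2%, 0 | 7.8% vs 4.0% | 1.96 | 15.8% vs 12.9% | 1.23 |
| 2%, 0.5 | 6.4% vs 3.7% | 1.74 | 10.1% vs 8.5% | 1.19 |
| 2%, 0.8 | 4.7% vs 3.2% | 1.48 | 6.2% vs 5.4% | 1.14 |
| 2%, 0.95 | 3.2% vs 2.6% | 1.24 | 3.7% vs 3.4% | 1.08 |
| 5%, 0.95 | 7.6% vs 6.3% | 1.21 | 8.5% vs 7.9% | 1.07 |

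The first and last rows are the extremes of the grid (p from 0.5% to 5%, ρ from 0 to 0.95). The correlation model matters: a beta-binomial with intraclass correlation 0.5 and p = 2% gives 4.1% vs 3.0% through C3D1, ratio about 1.4. As ρ approaches 1 the ratio approaches 1, because the next Day 1 draw also catches a persistent abnormality.

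**Dilution by early enrollment.** Suppose the 100 two-arm Arm A participants had no Day 15 tests (an inference). The ratio becomes 1 + (220/320)×(ratio−1), and the whole-treatment range falls from 1.07–1.24 to about 1.05–1.16.

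**What a common-visit table does.** Through C3D1 it leaves 2 draws against 2, so the ratio is 1.00 at equal toxicity and equal time on treatment. Over whole treatment it does not equalise draws if Arm A stays on longer. With q = exp(−28·ln2/(median × 30.4375)), mean draws are 1 + q/(1−q):

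- Median 4.3 months: q = 0.862, about 7.3 draws.
- Median 5.8 months (planned for Arm A): q = 0.896, about 9.6 draws.

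That gap of roughly 2.3 exceeds the 1.8 or so draws that Day 15 testing adds in Arm A at that median.

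**The case against.** The strongest case against acting has five parts.

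- **The size is unknown, and the early window is not the planned table.** This stands. A reader might infer from 7.8% versus 4.0% that the Arm A tables will show about twice the true relative toxicity. The documents do not support that: they give no event rates, and the planned tables run over all of treatment, where the same assumptions give at most 1.24.
- **No laboratory hypothesis is tested.** This stands. The objective concerns each arm's safety, the tables are descriptive, and they lie outside alpha control. It limits the consequence but does not make the columns comparable.
- **A Day-1-only table could err the other way.** This stands. Protocol Section 6.6.1 makes neutrophil and ALT/AST abnormalities on imlunestrant follow its dose-adjustment table whether or not they are clinically significant. A Day 15 value may therefore lead to action that lowers the next Day 1 grade. A reader might conclude that the restricted table should carry the between-arm statement; for this reason, and because of the unequal draw counts over whole treatment, it should not.
- **Some handling exists.** This stands in part. SAP Section 4.1.1 allows analysis visits for by-visit work where judged appropriate, abnormal values will be listed, and Protocol Appendix 4 allows additional tests at any time, which could narrow the gap. None is a committed common-visit laboratory summary. The repeat liver testing in Protocol Section 8.2.2.1 could also widen the gap, since a qualifying Day 15 elevation generates further Arm A values.
- **Not all of Arm A may have had four draws.** This stands as an inference. Amendment (a) added visits, and the country layouts for Belgium, Germany and Italy in Appendix 10 show Day 15 in Cycle 1 only. The effect is diluted, not removed.

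**Conclusion.** The concern holds in a limited form. The scheduling asymmetry is explicit, and the SAP's statistic is sensitive to it. The A versus B laboratory tables are liable to overstate transient abnormalities in Arm A.

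Under equal assumed per-draw rates the artificial ratio is about 1.2 to 2.0 through Cycle 3 Day 1, about 1.05 to 1.24 over whole treatment, and near 1 for persistent abnormalities. The whole-treatment range rests on the assumed p and ρ and on equal exponential time on treatment with median 4.3 months; its lower end also assumes no Day 15 tests in the two-arm stream.

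PFS, OS and type I error are unaffected. A reader might also infer that C versus A is entirely free of the problem. The Day 15 schedule is the same in those arms, but the laboratory tables use the safety population, which is not limited to concurrently randomized participants. Arm A patients enrolled before amendment (a) may lack some of these draws. This is a cheap improvement to the SAP, not a flaw in the trial's primary conclusions.

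**What to change.** In SAP Section 4.4.2:

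1. Keep the all-data worst-grade and shift tables as the main display.
2. For Arm A versus Arm B, add a supplementary set restricted to visits scheduled in every arm: Day 1 of each cycle and short-term follow-up. Preferably also give it over a common early window, such as through Cycle 3 Day 1, so that longer time on treatment does not bring the imbalance back.
3. Report the number of post-baseline draws per arm.

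The cost is a few lines of SAP text and one extra set of tables. Monitoring and data collection do not change. The downside should be stated with the tables: they omit Day 15 findings and may understate Arm A toxicity where a Day 15 value led to a dose adjustment. They should be read alongside the all-data tables and not replace them.

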1.3.1. Schedule of Assessments for Patient-Reported Outcomes

Instrument	Screening	Cycle 1	Complete		during All Cy isit (SFU)	cles until Last	Short-Term Follow-Up	Instructions
Visit Window		Day 1	Every Day	Every Week	Every 4 Weeks	Every 8 Weeks		
EORTC IL 19 ª						Х		The first administration of EORTC IL-19 will occur on C2D1, completed electronically by the patient at home, not site-administered, and then every 8 weeks thereafter. EORTC IL 19 will not be administered during the STFU visit. EORTC QLQ-C30 and EORTC IL 19 instruments will be administered on an alternating schedule such that these are scheduled about 4 weeks apart from each other due to the overlapping items for physical function.
PGIS		X			Х		Х	Completed at home every 4 weeks on ePRO patient hand-held device, except on C1D1 and SFU when it will be administered in the clinic.
EQ-5D-5L		Х				Х	Х	Completed electronically every 8 weeks by the patient. Administered at home on ePRO patient hand-held device, except on C1D1 and SFU when it will be administered in the clinic.

Abbreviations: C = cycle; D = day; EORTC IL 19 = European Organization for Research and Treatment of Cancer Item Library 19; EORTC QLQ-C30 = European Organization for Research and Treatment of Cancer Quality of Life Questionnaire-Core 30; EQ-5D-5L = 5-level-EuroQol; mBPIsf = modified Brief Pain Inventory-short form; NRS = numeric rating scale; PGIS= Patient's Global Impression of Symptoms; PROs = patient-reported outcomes; PRO-CTCAE = Patient Reported Outcomes - Common Terminology Criteria for Adverse Events; STFU = short-term follow-up.

^a EORTC IL 19 will not be administered during the weeks that EORTC QLQ-C30 is administered due to overlapping items.

1.3.2. Sampling Schedules for Pharmacokinetics

The schedule for PK sampling for patients receiving treatment with imlunestrant (Arm A) or imlunestrant plus abemaciclib (Arm C) on study is summarized in the table below. PK samples collected in Arm A will be analyzed for imlunestrant concentrations. PK samples collected in Arm C will be analyzed for concentrations of both imlunestrant and abemaciclib (and its metabolites). See also fasting requirements for imlunestrant dosing in Section 6.1.

On all PK sampling days (with the exception of Cycle 3 Day 1), patients should take the study drug at the clinic. The date and exact time of collection for each venous blood sample should be documented on the laboratory requisition. Differences from the time specified in the protocol are not considered protocol deviations if samples are collected and accurate dates and times are recorded in a timely manner on the appropriate forms.

Cycle	Day	PK Sample Number	ECG Sample Number ^a	PK Sampling Time Relative to Imlunestrant Dosing
Screening	Day -28 to Day -1		1	
Cycle 1	Day 1	1	2	2 to 4 hours postdose
Cycle 2	Day 1	2	3	Predose ^b
Cycle 3	Day 1°	3		PK draw should occur approximately 3 hours after study drug dose. For flexibility, the patient may take C3D1 dose at home prior to arrival at site.
	Day 1°	4		2 ± 0.5 hours after PK Sample Number 3 (at least 5 ± 0.5 hours after taking study drug dose at home)
Cycle 4	Day 1	5	4	Predose ^b
Short-term follow-up	30-Day follow-up		5	

Pharmacokinetic Sampling Schedule for Arm A and Arm C

Abbreviations: ECG = electrocardiogram; PK = pharmacokinetic.

- ^a A local ECG (no replicates required) should be obtained at baseline in all patients, 2 to 4 hours after the imlunestrant dose on Cycle 1 Day 1, pre-imlunestrant dose on Cycle 2 Day 1, and Cycle 4 Day 1, and at the short-term follow-up visit. Predose ECGs should be taken at either 90 (-90) minutes, 60 (-60) minutes, or 30 (-30) minutes. Predose time points are flexible for site convenience.
- ^b Predose PK samples should be taken within 90 minutes prior to next dose.
- ^c On Cycle 3 Day 1 only, patient may take study drug dose at home before arrival at site. The time of study drug dose intake must be recorded by the patient that day.

2. Introduction

Breast cancer is the most frequent cancer among women and is a major cause of cancer-related deaths worldwide. It is estimated that more than 2 million new cases of breast cancer occurred worldwide in women in 2018 (Bray et al. 2018). Treatment options for women with breast cancer are largely determined by tumor hormone receptor (HR) and HER2 status (Gradishar et al. 2020; Waks and Winer 2019).

Over two-thirds of breast cancers express the ER, which is a key driver of breast cancer initiation and progression. ER+ mBC is incurable and therefore considered a serious and life-threatening disease, with a median OS of only 2 to 3 years (Cardoso et al. 2012; Sledge 2020). For patients with HR+, HER2- status, treatment options include ET given alone or in combination with a CDK4/6 inhibitor (abemaciclib, palbociclib, ribociclib); an mTOR inhibitor (everolimus), or a PI3K inhibitor (alpelisib, for the subset of tumors also harboring select PIK3CA mutations). Alternatively, some patients may receive chemotherapy (for example, capecitabine, docetaxel, paclitaxel, nab-paclitaxel (Waks and Winer 2019; Gradishar et al. 2020) as initial therapy based on aggressiveness at initial presentation, or as salvage therapy following failure of ET-based interventions. However, in most ER+ breast cancers, ER remains an important therapeutic target even after the development of resistance to initial ET and changing the ET backbone has led to improved outcomes, either alone or with other anticancer therapies (Weatherman et al. 1999; Baselga et al. 2012; Turner et al. 2015; Finn et al. 2016; André et al. 2019).

Multiple means of inhibition of ER signaling are already available. These include strategies such as direct ER modulation (tamoxifen), systemic prevention of the conversion of androgens to estrogens using AIs, and SERDs (fulvestrant) that block and degrade the ER. While ET is typically highly effective initially, especially with the incorporation of CDK4/6 inhibitors (Finn et al. 2016; Hortobagyi et al. 2016; Goetz et al. 2017), most patients ultimately relapse and develop acquired ET resistance (Lei et al. 2019). Outcomes for subsequent second-line ET, often with fulvestrant or exemestane, are unfortunately poor and remain an area of unmet need (Chia et al. 2008).

It is now understood that an important mechanism to the development of ET resistance is the acquisition of somatic mutations in the ER gene (*ESR1*) (Robinson et al. 2013; Toy et al. 2013; Jeselsohn et al. 2014). These mutations result in a ligand-independent constitutively activated ER, leading to proliferation and decreased sensitivity to ET. These mutations in *ESR1* have been observed in anywhere up to 50% of mBC patients with the rate highest in patients treated with multiple lines of ET (Zundelevich et al. 2020). Importantly, both preclinical and clinical data demonstrate that SERDs can continue to exert antagonistic effects even in the presence of select *ESR1* mutations (Toy et al. 2017, Turner et al. 2020), ultimately leading to downregulation of the constitutively active receptor.

Fulvestrant is currently the only regulatory agency-approved SERD for the treatment of ER+ mBC (Nardone et al. 2019). However, it has limitations. Due to its insoluble nature with poor oral bioavailability and a short intravenous (IV) half-life, fulvestrant needs to be given IM and is

highly dose dependent (Robertson and Harrison 2004; Robertson et al. 2004). Certainly, improved outcomes were observed in patients receiving a dose of 500 mg IM compared to 250 mg IM (Di Leo et al. 2014). Even though doses higher than 500 mg per month may lead to better ER degradation, the IM administration route of fulvestrant limits the amount of fulvestrant that can be given to patients. Moreover, studies have shown that the maximum administrable dose of 500 mg remains insufficient for maximal ER downregulation in patients. Certainly, patients with inadequate ER downregulation to fulvestrant do appear to do significantly worse than those with a greater decrease in ER, as measured by reduction in ER availability on FES-PET (van Kruchten et al. 2015).

Therefore, there is unmet medical need to develop novel ETs, such as oral SERDs to overcome both the resistance and the PK limitations of fulvestrant, to offer improved bioavailability, greater ER-targeting and -degradation capabilities (Nardone et al. 2019).

Introduction/Rationale for Amendment (a): Addition of Study Arm C (Imlunestrant plus Abemaciclib)

The incorporation of CDK4/6 inhibitors with ET into first line treatment of HR+, HER2- MBC has dramatically improved outcomes (Finn et al. 2016, Tripathy et al. 2018, Johnston et al. 2019). Additionally, the monarchE trial demonstrated significant and clinically meaningful improvement in IDFS and DRFS with the addition of abemaciclib to adjuvant endocrine therapy (ET) (Johnston et al. 2020).

However, resistance mechanisms to CDK4/6 inhibitor regimens are not well understood and may be multifactorial, including resistance to the ET backbone and/or the CDK4/6 inhibitor. Specifically, tumors that have developed endocrine resistance (e.g., through an *ESR1* mutation, a common mechanism of acquired ET resistance), may still have continued dependence on inhibition of the CDK4 and 6 pathway. Given the safety and tolerability of CDK4/6 inhibitors in combination with ET, there is growing interest in testing the continuation of a CDK4/6 inhibitor beyond progression while switching the ET backbone. In fact, some randomized Phase 2 studies of continued CDK4/6 inhibition are ongoing to address this question (NCT02632045, NCT03147287, NCT03809988). Supporting this hypothesis, there is preclinical data demonstrating synergy of abemaciclib plus fulvestrant in cell lines resistant to CDK4/6 inhibitors (data on file) along with real-world retrospective clinical studies suggesting the benefit of abemaciclib following disease progression on a CDK4/6 inhibitor (Wander et al. 2020, Martio et al. 2020).

Study J2J-OX-JZLC (henceforth referred to as EMBER-3) is a Phase 3, randomized, 3-arm study of imlunestrant, Investigator's Choice of Endocrine Therapy of either fulvestrant or exemestane, and Imlunestrant plus Abemaciclib for patients with ER+, HER2- locally advanced or metastatic breast cancer previously treated with an AI, with or without a CDK4/6 inhibitor. This study will evaluate 2 comparisons: Imlunestrant vs Investigator's Choice of Endocrine Therapy; and Imlunestrant plus Abemaciclib vs Imlunestrant.

Introduction/Rationale for Amendment (b): Addition of the PFS of Arm A to Arm B in the *ESR1*-mutation detected population as a primary endpoint

The primary goals of this trial are to determine whether: imlunestrant prolongs PFS compared to Investigator's Choice of Endocrine Therapy in patients with ER+, HER2- locally advanced or mBC previously treated with an AI with or without a CDK4/6 inhibitor; AND if imlunestrant plus abemaciclib prolongs PFS compared to imlunestrant monotherapy (inferentially tested ONLY if the PFS between Arm A and Arm B is statistically significant).

It is well understood that a proportion (up to approximately 50%) of the unselected enrolled population (ITT population) will have an *ESR1*-mutation detected at baseline (*ESR1*-mutation detected population) (Zundelevich et al. 2020). Analyses in this subpopulation were already prespecified in the initial study protocol. However, with this amendment (amendment b), the analysis of PFS in the *ESR1*-mutation detected population now will be elevated to a primary endpoint, based on evolving data among the novel SERD class showing increased clinical benefit with *ESR1*-mutation enrichment (Bidard et al. 2022). With the proposed statistical methodology to adjust for multiplicity, the trial will be considered to have met its primary objective (for the Arm A to Arm B comparison) if imlunestrant is superior to Investigator's Choice of Endocrine Therapy in PFS in either all patients (ITT) OR in patients with an *ESR1*-mutation detected (*ESR1*-mutation detected population).

Introduction/Rationale for Amendment (c): Increasing the sample size for PFS between Arm A and Arm B

In this amendment, the total sample size for Arm A and Arm B has been increased to approximately 640 participants (320 in each arm). The primary analysis of PFS between Arm A and Arm B in the ITT population will be conducted when approximately 480 events have been observed (maintaining the same censoring rate of 25% as before). With a total of 480 events, the statistical power has been increased from 80% to 89% assuming a target hazard ratio of 0.74. Correspondingly, the required number of events for PFS between Arm A and Arm B in the *ESR1*-mutation detected population has also been increased from approximately 150 to 192, resulting in increased statistical power (from 80% to 90%) for this endpoint as well.

Additionally, all three arms will be closed at the same time (once the target enrollment for Arm A and Arm B is met). The estimated total sample size across all three arms has increased from approximately 800 to 860 under the updated enrollment assumptions.

Introduction/Rationale for Amendment (d): Updating initial alpha allocation for PFS between Arm A and Arm B

In this amendment, the initial alpha allocation for PFS between Arm A and Arm B in the ITT population (H_1) and PFS between Arm A and Arm B in the *ESR1*-mutation detected population (H_2) is updated from 0.02 and 0.005 to 0.005 and 0.02, respectively. This update is based on the external data of oral SERDs in patients with recurrent ER+ HER2 negative breast cancer where clinically and statistically meaningful improvement in PFS has been primarily driven by the

ESR1-mutation detected population (Bidard et al. 2022). In addition, the second interim analysis for efficacy for H_1 (interim 2) has been removed since the timing of interim 2 is projected to be closer to the timing of the final analysis based on the updated enrollment projection.

